Title: To evaluate the utility of NETSPOT Imaging in Head and Neck Cancer Patients

Date: December 28, 2017

NCT# NCT03602911

Investigator Initiated Study Proposal

Proposed Study Title

Study Title: To evaluate the utility of NETSPOT Imaging in Head and Neck Cancer Patients

Request Date: 12/28/2017

Principal Investigator Contact Information

Name: [name]

Title: MD

Address: [name]

City, State, Zip: [name]

[contact]

E-mail: [contact]

Contracting Information (if applicable)

Name:

Phone/Fax:

E-mail:

Study Information

Indication: Enrollment criteria include all patients with head and neck cancer undergoing ¹⁸F FDG PET/CT at time of primary diagnosis or after completion of therapy.

Line of treatment:

Phase: Preliminary

Number of Subjects: 30

Background and Rationale:

Provide background (including references) on unanswered question(s) the study is attempting to answer

Head and neck squamous cell carcinoma (HNSCC) makes up 90% of head and neck cancers. The incidence is increasing, in part due to the human papilloma virus (HPV), a well-established factor in the development of HNSCC. Unfortunately, tumor-specific imaging for HNSCC and HPV-related HNSCC are non-existent, making detection and follow-up reliant on surrogate markers for metabolic activity. ¹⁸F FDG Positron Emission Tomography (PET), combined with computerized tomography (PET/CT), is the current standard for imaging in HNSCC. Specifically, ¹⁸F FDG PET/CT is used for patients with advanced stage disease, those with unknown primary site, and as part of the post-treatment imaging. ¹⁸F FDG PET/CT has a high sensitivity, but the specificity can be limited in patients with underlying inflammation, infection, or after radiation therapy. As such, tumor-specific imaging has the potential to improve detection of de novo and/or recurrent tumors in this high risk population.

Interestingly, HNSCCs have been found to express somatostatin receptors (SSTRs). SSTRs have also been found in laryngeal cancer specimens and cancers of the oral cavity and oropharynx, but not in control tissue^{1,2}. Recent studies have found that HPV causes mutations in the same pathways that activate SSTR expression on tumor cells³. These studies suggest a correlation with HPV-positive HNSCC and SSTR expression. This latter group of patients often have non-detectable primary tumors that arise from the oropharynx, an area that normally exhibits ¹⁸F FDG PET/CT uptake thus making tumor localization difficult. Schartinger et al studied SSTR PET/CT in a small series of HNSCC patients and found that all patients showed radionucleotide uptake on imaging⁴. Multiple case reports have been published showing similar uptake for head and neck squamous cell carcinomas by ⁶⁸Ga^{5,6}. An unpublished trial was performed comparing SSTR PET/CT with ¹⁸F FDG PET/CT for 35 patients with HNSCC; the study concluded that SSTR PET/CT had the potential to be more specific for HNSCC than ¹⁸F FDG PET/CT⁷. Unfortunately the study was small, HPV status was not correlated, and recurrent/post-treatment patients were not studied. These studies show that SSTR-specific imaging, such as NETSPOT, has the potential to be equal to and possibly more specific than ¹⁸F FDG PET/CT for HNSCC patients, especially in the setting of HPV positivity, unknown primary site tumors, and post-treatment follow-up. More importantly, a therapeutic target for SSTRs is widely available; as such, HNSCC patients who show clinical uptake on NETSPOT imaging may be candidates for future studies using targeted therapeutics.

Objectives and study aims:

List the primary/secondary objectives to correspond directly with the listed hypotheses; define the role of AAA compounds

Study Aim:

Evaluate utility of NETSPOT imaging for disease detection in HNSCC, as well as the potential for targeted receptor-specific therapeutics.

Primary Objectives:

To determine the utility of NETSPOT imaging, as compared to ¹⁸F FDG PET/CT, in detection and staging of HNSCC.

To evaluate the potential of NETSPOT imaging in guiding the use of targeted radiopeptides for HNSCC treatment.

Secondary Objectives:

To determine if NETSPOT imaging and ¹⁸F FDG PET/CT, when used together, can lead to improved tumor delineation and detection of metastatic disease.

To determine the imaging characteristics of NETSPOT versus ¹⁸F FDG PET/CT in the setting of inflammation.

To determine if NETSPOT imaging uptake correlates with tumor HPV-positivity.

To determine if patients with tumor uptake on NETSPOT imaging exhibit different disease outcomes than patients without uptake.

Hypothesis:

List the clinical hypotheses in order of priority

NETSPOT imaging will be at least equivalent to ¹⁸F FDG PET/CT in the detection and staging of HNSCC.

The combination of NETSPOT imaging and ¹⁸F FDG PET/CT, will have increased specificity for detecting the primary site for HNSCC of unknown primary than ¹⁸F FDG PET/CT alone.

The combination of NETSPOT imaging and ¹⁸F FDG PET/CT, will have increased specificity for detecting disease recurrence and metastasis following treatment than ¹⁸F FDG PET/CT alone.

Is a study protocol already available (Yes/No)? If yes, please attach to the IIS form

No.

Study Design/Clinical Plan:

Provide a concise overview stating the type of experimental design (for ex, randomized/non-randomized, condensed eligibility criteria etc)

Design: This study will be designed as a “proof-of-concept” trial to compare NETSPOT with ¹⁸F FDG PET/CT for HNSCC.

Inclusion Criteria:

HNSCC patients undergoing planned ¹⁸F FDG PET/CT at time of primary diagnosis.

HNSCC patients undergoing planned ¹⁸F FDG PET/CT for unknown primary site.

HNSCC patients undergoing planned ¹⁸F FDG PET/CT after completion of adjuvant treatment.

Exclusion Criteria:

Inability to undergo ¹⁸F FDG PET/CT imaging due to medical comorbidities.

Enrollment:

Patients meeting inclusion criteria will be enrolled on evaluation. Based on our current clinical volume, we plan to enroll 30 patients over a 6 month time frame.

Preliminary analysis (outlined below) will be done after the first 30 patients to assess the utility of NETSPOT imaging in HNSCC.

Treatment:

List the clinical dosage/dosage form, route, and dose regimen

Brief Overview:

Patients meeting inclusion criteria will be consented at the time of scheduling.

All patients will undergo ¹⁸F FDG PET/CT per established protocol.

Following ¹⁸F FDG PET/CT, the patient will undergo NETSPOT imaging with the AAA-provided dose. These scans will be performed no less than 24 hours, no more than 7 days apart.

Analysis:

Both ¹⁸F FDG PET/CT and NETSPOT images will be reviewed by the senior radiologist and the primary surgeon for concordance between images. SUV will be measured for both images and recorded.

Patients will undergo clinical follow-up based on ¹⁸F FDG PET/CT results as per protocol.

True positive results will be recorded for both ¹⁸F FDG PET/CT and NETSPOT images and analyzed for sensitivity and specificity.

For patients undergoing surgical treatment, pathology results including routinely reported HPV markers will be recorded and compared to NETSPOT imaging characteristics.

Follow-up

All enrolled patients will be followed for 1 year after imaging.

Expected Results/Outcomes:

We expect that ¹⁸F FDG PET/CT and NETSPOT will have similar uptake and specificity for primary tumor. We hypothesize that NETSPOT will have increased specificity for unknown primary site tumor and recurrent or metastatic disease. Finally, we hope that NETSPOT positivity in HNSCC will allow for future study of targeted radionuclide therapies for HNSCC.

Applicability of Results:

Any other information regarding the medical need and/or the strategic importance of the research which may help the committee's evaluation

A proof-of-concept trial to compare SSTR/ PET/CT with ¹⁸F FDG PET/CT in the head and neck cancer population would be a novel use of the NETSPOT technology. The study is warranted based on past data and the potential for success, especially in patients with oropharyngeal tumors, previous radiation or inflammatory disease; all of whom ¹⁸F FDG PET/CT is difficult to interpret. If the hypothesis is supported, Advanced Accelerator will have a new application for the NETSPOT technology and a new area for business development and revenue.

Additional Research (if applicable):

Histology, biomarkers, PK etc.

Statistical Plan:

Include justification for clinical sample size and primary hypothesis testing

Statistical Considerations:

The primary objective of this study is to evaluate SSTR receptor expression in the head and neck cancer population. The secondary objective is to assess the concordance based on SSTR PET/CT with and without FDG PET/CT outcomes.

A Student t-test will be used to assess the difference of SSTR expression between the diagnostic results (positive vs negative) and Fisher's exact test will be used to assess the association between dichotomized expression (high vs low) and a binary outcome (positive vs negative). The sensitivity will be estimated by a proportion of true positives that are correctly identified by the new method. The specificity will be estimated by a proportion of true negative that are correctly identified by the new method. The corresponding 95% confidence intervals will be estimated based on binomial distributions.

Sample Size: Based on the two-sided t-test, a sample size of 30 will have 81% power to detect 0.95 standard deviations of the SSTR expression between positive and negative outcomes (15 per group) at a 0.10 significance level. In addition, based on the historical data and current literatures, head and neck squamous cell carcinoma (HNSCC) makes up 90% of head and neck cancers. For primary tumor detection, 18F FDG PET/CT is about 96% sensitive (oral cavity only) and anywhere from 91%-98% accurate at detecting lymph node metastasis, with sensitivity of 67%-79%, and specificity of 82-95%. For detecting recurrent disease, 18F FDG PET/CT is ranged from 83%-100% sensitive and 90-98% specific. Based on one-sided non-inferiority test for two correlated proportions with a concordance of 0.90, when the maximum allowable difference between these proportions that still results in non-inferiority (the range of non-inferiority) is 0.15, a sample size of 30 subjects achieves 81% power at a significance level of 0.10.

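### The non-inferiority power statement counts all 30 enrolled patients as pairs without naming the proportion compared; tumour-free post-treatment patients then either dilute the 0.15 margin or leave power short of 81%

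*Combined protocol and SAP*

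**What the plan says.** The first-ranked entry under Hypothesis is that "NETSPOT imaging will be at least equivalent to ¹⁸F FDG PET/CT in the detection and staging of HNSCC". Inclusion Criteria lists three groups: primary diagnosis, unknown primary site, and "HNSCC patients undergoing planned ¹⁸F FDG PET/CT after completion of adjuvant treatment". The third does not require known or suspected recurrence. One total covers all three groups ("we plan to enroll 30 patients over a 6 month time frame"), with no quota, stratum or analysis set.

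The Sample Size paragraph relies on a "one-sided non-inferiority test for two correlated proportions with a concordance of 0.90" and a maximum allowable difference of 0.15, and concludes that "a sample size of 30 subjects achieves 81% power at a significance level of 0.10". It does not say whether the two proportions are positivity, accuracy or sensitivity. Statistical Considerations defines sensitivity and specificity separately, each conditional on true disease status. The non-inferiority test is not among the analyses listed there.

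**The concern.** A tumour-free patient who is negative on both scans forms a concordant pair. That pair says nothing about whether NETSPOT finds tumour. If it is counted, it enlarges the denominator to which the 0.15 margin applies, so a larger loss of sensitivity fits inside the margin. If it is not counted, the test has fewer than 30 pairs and the stated power does not apply. The plan does not choose between these, and nothing limits how many of the 30 come from the post-treatment group. At stake is whether a finding of at least equivalent detection would mean what the 0.15 margin and the 0.10 error rate suggest.

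**Working it through.** **Inputs from Sample Size:** n = 30, margin m = 0.15, concordance 0.90 (discordance 0.10), one-sided alpha 0.10 (z = 1.2816).

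**Inputs assumed:** the tumour-bearing share D, and NETSPOT-only detections in 2–5% of tumour-bearing patients.

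**Step 1: reproduce the 81%.** Use the score test for paired proportions with no true difference, so discordance splits 0.05 + 0.05.
- The restricted estimate q solves 2q² − (0.10 + 2m)q + 0.05·m(1 + m) = 0. So q = [0.40 + √(0.16 − 0.069)]/4 = 0.1754.
- Null variance per pair = 2q − m(1 + m) = 0.3508 − 0.1725 = 0.1783. True variance per pair = 0.10.
- Power = Φ[(0.15·√30 − 1.2816·√0.1783)/√0.10] = Φ[(0.8216 − 0.5412)/0.3162] = Φ(0.887) = 81.2%.
- Exact enumeration gives 81.1%.

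The Wald version gives 90.6% (87.3% enumerated), so the score test is the one that matches. The match uses 30 pairs, that is, every enrolled patient.

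**Step 2: reading A, a per-patient result over all 30.** Suppose tumour-free patients are negative on both scans. A sensitivity loss s among tumour-bearing patients then appears as D·s in the pooled comparison, so the margin allows s = 0.15/D. The last three columns give the enumerated chance of declaring non-inferiority, with the number of tumour-bearing patients fixed. Each range runs from 2% to 5% NETSPOT-only detections.

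| Tumour-bearing of 30 | D | 0.15/D | True loss 0.15 | True loss 0.20 | True loss 0.30 |
|---|---|---|---|---|---|
| 30 | 1 | 0.15 | 8–9% | 2–3% | under 1% |
| 24 | 0.80 | 0.19 | 14–16% | 6–7% | about 1% |
| 20 | 0.67 | 0.225 | 21–23% | 10–12% | about 2% |
| 15 | 0.50 | 0.30 | 33–34% | 19–22% | 5–7% |

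Treating D as a probability instead of a fixed count changes these by about one point at most (34.1% instead of 33.0% at D = 0.50, loss 0.15).

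**Step 3: which observed results pass.** With 30 pairs, no table with two or more net NETSPOT misses passes. The closest, 0 NETSPOT-only against 2 FDG-only, gives 1.278, just under 1.282. A pass therefore means at most one net miss, which is 1/15 = 6.7 points observed at D = 0.50.

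**Step 4: FDG false positives.** Let FDG be falsely positive in 10% of tumour-free patients (the low end of the 90–98% specificity quoted for recurrence) and NETSPOT in none. Take a true loss of 0.15, 2% NETSPOT-only detections and D as a probability. At D = 0.67 and 0.50 the chance of passing is:
- positivity endpoint: 10% and 12%
- accuracy endpoint: 39% and 62%

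**Step 5: reading B, sensitivity as the plan defines it.** Only tumour-bearing patients enter. At concordance 0.90 and no true difference, power (enumerated; asymptotic in brackets) is:
- 24 patients: 74.1% (73.0%)
- 20 patients: 64.7% (65.9%)
- 15 patients: 66.1% (55.0%)

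The enumerated value at 15 exceeds that at 20 because so few tables exist. The test also runs above its nominal level there: 11.6–12.4% at a true loss of 0.15, against 7–10% with 20.

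**The case against.** Much of the opposing case stands.

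- The dilution depends on an endpoint that the plan never names. Under the plan's own definition of sensitivity, tumour-free patients are outside the denominator and nothing is diluted. The point is therefore conditional. But that reading removes the 81%, so it does not rescue the statement.
- A reader might infer that a clearly less sensitive NETSPOT would pass. The figures do not support that. A true 30-point loss passes only 5–7% of the time even when half the cohort is tumour-free, and an observed deficit of two net misses always fails.
- A reader might infer that the bias always favours NETSPOT. That is not established either. The Background says FDG specificity can be limited after radiation or with inflammation. Such false positives count against NETSPOT on a positivity endpoint and hide its misses on an accuracy endpoint.
- A reader might infer that post-treatment patients do not belong in the lead hypothesis because recurrence has its own. The lead hypothesis is not limited to untreated disease, and the Background speaks of de novo and recurrent tumours. Unknown primary also has its own hypothesis. The recurrence hypothesis concerns the specificity of the two scans combined. Dropping the group would discard true recurrences, which do inform detection.
- The 15/15 split in the t-test calculation is by positive and negative outcome, so it does not establish the tumour-bearing share.
- This is a proof-of-concept study, and the non-inferiority test appears only in the sample-size justification. That lowers the stakes. It is still the only power statement that addresses the lead hypothesis.

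**Conclusion.** The concern holds in a conditional form. The plan's 81% requires all 30 patients as pairs, while eligibility admits patients who may have no tumour and the proportion is unnamed. On a whole-cohort proportion, the error rate at a true 15-point sensitivity loss goes from about 8% to 14–33% as D falls from 1 to between 0.80 and 0.50, if tumour-free patients are negative on both scans. With FDG false positives, its size and direction depend on the endpoint. On sensitivity as defined, power is about 65–74% with 15–24 tumour-bearing patients. These results rest on the score test, which the plan does not name but which reproduces its figure, and on an assumed D. The plan should be changed before the test is used, but the documents do not show that a grossly inferior scan would be likely to pass.

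**What to change.** - State that the detection non-inferiority test compares per-patient sensitivity in patients with tumour by the reference standard (pathology or the planned one-year follow-up), from any inclusion group.
- Compare specificity separately in tumour-free patients.
- Record the qualifying inclusion criterion at enrolment and report results by inclusion group.
- Restate the power for the expected number of tumour-bearing patients instead of 30, and add the test to the listed analyses.

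This costs wording and one enrolment field. The downside is fewer pairs and a lower stated power. Keeping 30 tumour-bearing pairs, and so 81%, would need about 30/0.80 = 38, 30/0.67 = 45 or 30/0.50 = 60 enrolled at those assumed shares. If enrolment stays at 30, the lower power should simply be reported.

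### The lead hypothesis claims NETSPOT is equal to or better than FDG PET/CT, but the sized test can only rule out a 15-point loss at a one-sided 10% level, and the paired difference is not among the planned estimates

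*Combined protocol and SAP*

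**What the plan says.** The Hypothesis section is set out in order of priority, and its first entry states that "NETSPOT imaging will be at least equivalent to" FDG PET/CT for detecting and staging HNSCC.

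The only sizing that fits this comparison is the second calculation in the Sample Size paragraph of the Statistical Plan. It is introduced by "Based on one-sided non-inferiority test for two correlated proportions with a concordance of 0.90" and sets the margin with "when the maximum allowable difference between these proportions that still results in non-inferiority (the range of non-inferiority) is 0.15". It concludes that "a sample size of 30 subjects achieves 81% power at a significance level of 0.10".

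Statistical Considerations lists a t-test and Fisher's exact test on SSTR expression, then sensitivity and specificity of the new method. For the latter, "The corresponding 95% confidence intervals will be estimated based on binomial distributions". The Analysis section says true positives are recorded for both scans and analysed for sensitivity and specificity.

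The non-inferiority test appears only in the sample size paragraph. The plan does not say which proportion is tested, what true difference was assumed, why the margin is 15 points, or what conclusion a pass would permit.

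**The concern.** The hypothesis and the test make different statements. The hypothesis says NETSPOT loses nothing against FDG PET/CT. The test asks whether a loss of 15 points or more can be excluded. Without a rule linking the two, a pass could be reported in the words of the hypothesis. This matters because the Applicability of Results section ties a new application of NETSPOT to the hypothesis being supported, and the plan never says what supported means.

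The planned intervals do not fill the gap. A binomial interval for NETSPOT alone says how precisely NETSPOT's accuracy is known. It carries no information on how many patients were positive on one scan only, and that is what determines the paired comparison. Point estimates for both scans could be subtracted, but no interval for the difference is planned. The reader would therefore have no measure of how large a loss the data leave open.

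**Working it through.** **Inputs, all from the Sample Size paragraph.** N = 30; margin δ = 0.15; one-sided level 0.10; concordance 0.90, so discordance 1 − 0.90 = 0.10. Two assumptions are mine because the plan is silent: no true difference, and all 30 patients contribute to the tested proportion.

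**Test.** Let b be the number of patients positive on NETSPOT only and c the number positive on FDG only. The paired score statistic is

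T = [(b − c)/N + δ] / √[(2p̃ + δ − δ²)/N],

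where p̃ is the maximum likelihood estimate of the NETSPOT-only probability when the true difference is fixed at −δ. The trial passes if T ≥ 1.282. Power is the sum of the trinomial probabilities of all (b, c) that pass, with cell probabilities 0.05, 0.05 and 0.90.

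**Reproducing the plan's figure.** Exact enumeration gives 81.1% and the asymptotic formula 81.2%, so the stated 81% stands. The plan does not name its method. The alternatives tried do not match: Wald gives 87.3% exact and 90.6% asymptotic, and Wald with continuity correction gives 77.7%.

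**What a pass excludes.** The margin is an absolute 15 points. If the tested proportion is sensitivity, the edge of the margin against the plan's own FDG figures is:

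| Setting | FDG sensitivity in the plan | Less 15 points |
|---|---|---|
| Primary tumour (oral cavity only) | 96% | 81% |
| Lymph node metastasis | 67–79% | 52–64% |
| Recurrence | 83–100% | 68–85% |

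A pass speaks against values at or below the right-hand column. It does not establish the middle column.

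**A pass with an observed deficit.** Take b = 0 and c = 1. Then p̃ = 0 and T = (−1/30 + 0.15)/√(0.1275/30) = 0.1167/0.0652 = 1.79, a pass. NETSPOT is 1/30 = 3.3 points lower in the sample, and the lower limit of the 80% score interval is −10.5 points. That supports non-inferiority within 15 points, but not equal or better. With b = 0 and c = 2, T = 0.0833/0.0652 = 1.278, which just fails.

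**What the planned interval misses.** Suppose NETSPOT detects 27 of 30 in both cases just described. FDG then detects 28 in the first and 29 in the second. The planned interval for NETSPOT is identical (exact binomial 95%, 73.5% to 97.9%), yet one trial passes and the other fails. These counts are illustrations, not plan figures.

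**Power of the same test at other levels.**

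| One-sided level | Matching two-sided interval | Power |
|---|---|---|
| 0.10 (plan) | 80% | 81.1% |
| 0.05 | 90% | 68.9% |
| 0.025 | 95% | 53.1% |

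These hold for 30 contributing patients. The same enumeration at level 0.10 gives 81.7% with 25 and 64.7% with 20; the change is uneven because the counts are discrete.

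**The case against.** The strongest reply is that the Hypothesis section asks for clinical hypotheses, so its wording is an expectation and not a decision rule. The sample size paragraph openly states non-inferiority, the 0.15 margin, the one-sided test and the 0.10 level, and nothing says that a pass licenses the stronger wording. The study calls itself preliminary and a proof of concept, where a wide margin and relaxed level are legitimate. All of this is fair, and it is why the margin, level and sample size are not challenged here. It does not answer the point, because no conclusion from a pass is defined and the paired difference is not a planned estimate.

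Several stronger readings are tempting but not supported:

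- A reader might take it as a flaw that NETSPOT could pass when truly 5 points worse (51% of the time at discordance 0.10, 44% at 0.20). A 5-point loss lies inside the margin, so this is how a non-inferiority test is meant to behave. The 5 points is also not a plan figure.
- A reader might infer that a 15-point loss would readily pass. It would not: a true 15-point loss passes in 4.8% of trials at discordance 0.15 and 8.3% at 0.20, both below the nominal 10%.
- A reader might expect a pass to conflict with the reported 95% intervals. Those are one-sample intervals for NETSPOT. The plan has no 95% interval for the difference that could conflict.
- A reader might call the differing error levels inconsistent. They belong to different analyses and are disclosed.
- A reader might infer that NETSPOT is to replace FDG PET/CT. No section proposes this. Hypotheses 2 and 3 concern the two scans together, and clinical follow-up is based on FDG results.

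**Conclusion.** The point holds as a mismatch between claim and test, together with a missing estimate. A pass supports the statement that NETSPOT is not 15 or more points lower than FDG PET/CT, at a one-sided 10% level. It does not support equal or better. The listed analyses give no interval for the difference on which hypothesis 1 depends.

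There is no calculation error; the 81% reproduces. The power figures of about 69% at one-sided 0.05 and 53% at one-sided 0.025 rest on the paired score test, concordance 0.90, no true difference and all 30 patients contributing. If the tested proportion is sensitivity, only patients with disease count and the figures must be recalculated. The mismatch in wording and the missing interval depend on none of these assumptions.

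**What to change.** 1. Reword hypothesis 1, and state its permitted conclusion, as: NETSPOT is non-inferior to FDG PET/CT within 15 percentage points (one-sided 10% level) for the proportion being tested. Name that proportion.
2. Add the non-inferiority test and the paired NETSPOT-minus-FDG difference to Statistical Considerations. Report the difference with a paired score interval at 80% two-sided, which matches the test, and at 95%, for consistency with the other reported intervals.
3. Optionally, note beside the 81% that power is about 69% at one-sided 0.05 and 53% at one-sided 0.025 if all 30 patients contribute.

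The cost is a few sentences and one additional estimate from data already collected on both scans. Margin, significance level and sample size stay as they are. The downside is a weaker headline claim. With both intervals shown, a pass may also sit beside a 95% interval that reaches below −15 points; saying in advance that the 80% interval is the one tied to the test deals with that.

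### Hypothesis 2 claims specificity for the primary site in unknown-primary patients, who all have HNSCC, and the plan does not say what a true negative is in that group

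*Combined protocol and SAP*

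**What the plan says.** The Hypothesis section lists its hypotheses by priority. The second is that the two scans together "will have increased specificity for detecting the primary site for HNSCC of unknown primary", compared with FDG PET/CT alone. The corresponding entry under Inclusion Criteria is "HNSCC patients undergoing planned ¹⁸F FDG PET/CT for unknown primary site". The plan has no cancer-free comparison group.

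Statistical Considerations gives one estimator: "The specificity will be estimated by a proportion of true negative that are correctly identified by the new method". It adds: "The corresponding 95% confidence intervals will be estimated based on binomial distributions". It refers to the new method, whereas Hypothesis 2 is about the combination.

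On data, the Analysis section says: "True positive results will be recorded for both ¹⁸F FDG PET/CT and NETSPOT images and analyzed for sensitivity and specificity". On pathology it says: "For patients undergoing surgical treatment, pathology results including routinely reported HPV markers will be recorded and compared to NETSPOT imaging characteristics". All patients are followed for one year, but follow-up is not linked to classifying a scan as right or wrong.

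Nowhere does the plan state the unit of analysis (patient, site or lesion), the reference standard, what counts as a true negative for primary-site detection, how the two scans are combined, or which test compares the combination with FDG alone. The 30 patients span three inclusion groups, with no quota for unknown primary.

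**The concern.** Specificity needs units that are truly negative. In unknown-primary patients the cancer is already diagnosed and the open question is where it started. If the patient is the unit and disease is the target, nobody is negative. The Sample Size paragraph counts subjects and the intervals are binomial. Both point towards the patient as the unit, though neither says so.

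The analyst would then have to choose a definition after seeing the data. One choice gives an empty denominator. Another gives a percentage close to 100 whose size reflects the length of the site list. Neither tells a clinician how often the added scan points to the right place or the wrong one. The Background stresses that question, because normal FDG uptake in the oropharynx makes localisation hard.

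**Working it through.** **The plan's own figures.** Both power statements reproduce, and neither concerns Hypothesis 2.

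- Two-sided t-test, 15 per group, 0.95 SD, alpha 0.10: noncentrality 0.95 × √7.5 = 2.60 on 28 df gives power 0.814, against the stated 81%.
- One-sided paired non-inferiority, margin 0.15, concordance 0.90 (so discordance 0.10), alpha 0.10, n = 30, true difference 0. The restricted-likelihood score test has null variance 0.1783, so power = Φ[(√30 × 0.15 − 1.2816 × √0.1783)/√0.10] = 0.812. Exact enumeration gives 0.811, against the stated 81%.

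Neither calculation uses a count of true negatives.

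**Reading 1: patient as unit, target is presence of HNSCC.** By the inclusion criterion, true negatives = 0. Specificity is 0/0 and has no binomial interval.

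**Reading 2: tumour-free sites as negatives.** The documents give no site list and no subgroup size, so these inputs are assumptions: 10 patients, one true primary each, k candidate sites per patient, and 2 tumour-free sites wrongly marked in total.

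Negatives = 10 × (k − 1); specificity = (negatives − 2)/negatives.

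| k | Negatives | Specificity | Gap to a reading with no wrong sites |
|---|---|---|---|
| 5 | 40 | 38/40 = 95.0% | 5.0 points |
| 10 | 90 | 88/90 = 97.8% | 2.2 points |
| 20 | 190 | 188/190 = 98.9% | 1.1 points |

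The reads are identical in every row. Only the list length changes. A simple binomial interval would also treat the 40, 90 or 190 sites as independent, although they come from 10 patients.

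**Reading 3: patients with no primary found by the end of work-up and follow-up as negatives.** The denominator can exceed zero, but the documents give no count. If every such patient is read correctly, the exact 95% lower limit is 0.025^(1/n). For assumed counts, 3/3 gives 29–100%, 5/5 gives 48–100% and 10/10 gives 69–100%. This reading also credits a scan for marking nothing in a patient who has cancer.

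**Combination rule.** If the combination is positive when either scan is positive, it is negative only when both are. Its specificity then cannot exceed that of FDG alone, and Hypothesis 2 could not be true. Under the same rule a localisation rate could only stay equal or rise. The rule can therefore settle the direction of the result, and the plan states none.

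**The case against.** A reader might infer that this group contains no true negatives of any kind and that Hypothesis 2 is impossible to evaluate. The documents do not support that. The hypothesis concerns the primary site, false-positive sites can occur in patients with cancer, and the plan never fixes the unit. Readings 2 and 3 both give a computable figure once they are defined.

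A reader might also infer that the plan collects nothing on localisation. That too goes further than the text. True positives are to be recorded for both scans and pathology for surgical patients. If a true positive meant the correct primary site, the planned sensitivity would be close to a correct-site rate. What is missing is the definition.

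A third objection is that Hypothesis 2 is comparative and the same site list would apply to both readings. This stands in part. List length does not change which reading has fewer wrong sites, nor the paired discordant counts. It does change the absolute specificities and the size of the gap between them, and the plan names no paired comparison for the combination.

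The clustering criticism applies only if sites become the unit, which the plan does not say.

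Finally, this is a preliminary proof-of-concept proposal that states no protocol yet exists, and missing definitions affect its other accuracy estimates too. That limits the weight of the point. It does not remove it, because one natural reading of the estimator leaves this group with an empty denominator for the second-ranked hypothesis.

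**Conclusion.** The point holds in a limited form. Hypothesis 2 is not usefully estimable as written, though it is not inherently impossible to evaluate. With presence of disease as the target, the planned estimator is 0/0 at patient level, and the plan defines no other negative. With tumour-free sites as negatives, the absolute value is arbitrary: 95.0% to 98.9% for the same reads in the illustration, which rests on the assumed 10 patients, 2 wrong sites and 5 to 20 candidate sites. Simple binomial intervals would also ignore clustering.

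The zero denominator rests on the inclusion criterion alone. Both stated power figures are unaffected. The change should be made before images are read, because the site calls must be recorded as reading proceeds.

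**What to change.** In Hypothesis 2 and Statistical Considerations, replace specificity for the unknown-primary group with two paired per-patient measures of equal standing, so that the false-positive question is kept:

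1. the share of patients whose single best-site call matches the primary site confirmed by pathology;
2. the share of patients with a wrong site marked.

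Supporting rules:

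- **Reading order.** The same readers record a best-site call on FDG alone, then one joint call on FDG plus NETSPOT. Do not use an either-scan-positive rule. The combination can then do better or worse than FDG.
- **Unconfirmed primaries.** Patients with no confirmed primary by one year count as not localised for both readings. Sites marked in them are reported separately as unconfirmed.
- **Analysis.** Give exact 95% intervals and the paired discordant counts. Exact McNemar should be descriptive only, because the group has no quota within the 30 patients. Even with all discordant patients in one direction, 5 give a two-sided p of 2 × 0.5⁵ = 0.0625 and 6 give 2 × 0.5⁶ = 0.031.
- **Where specificity stays.** Keep it for post-treatment patients, among whom disease-free patients can exist.

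The cost is rewording one hypothesis and part of one paragraph, and naming the two site calls and the confirmed site as recorded items. No extra procedures or staff are needed. The downside is that patients whose primary is never confirmed lower both localisation rates. Pathology is promised only for surgical patients and follow-up is driven by the FDG result, so the number without confirmation should be reported.
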